Participants will be assessed at three times during treatment (weeks 1, 7, and 15), all of which will occur during the first semester. At the end of the academic year (April of spring semester), students will complete a final 5-month follow up assessment to test durability of treatment effects. The study will also test longer-term (17-month) efficacy in a random subsample of 20% of participants in Years 2-4, which will occur at the end of participant's sophomore year. While an extended follow up assessment of all N=540 participants is beyond the scope of the project, the longer follow-up on a random subsample of participants will provide an initial indication of longer-term efficacy. The 17-month follow up will yield approximately n=100 participants (n=50 BA condition and n=50 standard orientation condition).

Assessments during the intervention (weeks 1, 7, and 15) will be conducted in the classrooms in which the courses will be run, to facilitate participation. At follow up(s), participants will be contact via text and email and scheduled to attend the follow up assessment(s) at a study lab, which is located centrally on campus. Participants will be provided an escalating incentive schedule to maximize attendance at follow up(s), as described below.

Incentives

Participants will receive extra credit in their UNIV 101 course for participating in Assessments 1-3, and will be compensated \$50 for completing Assessment 4, which will occur after the courses have finished. To ensure participation in the research will not be coerced, students will be offered alternative extra credit assignments that will require approximately the same amount of time as participating in the study. The subsample of students participating in Assessment 5 (17-month follow up) will receive \$75 for completing the final assessment.

Research Staff

Research assistants who will collect study data will not be affiliated with the courses and will be blinded to study condition. Likewise, clinical staff who lead the course sections will not be

involved in research assessment administration and will be blind to participant responses.

Course and Intervention Content

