Treatment fidelity. Audio recordings of treatment will be rated by independent raters (e.g., raters not otherwise associated with the treatment delivery) to assess instructor adherence to and competence with the treatment protocol, using separate rating checklists and scales developed for the SO and BA protocols. Two senior research assistants will be trained in BA components to perform therapist adherence checks. They will review 20% of all audiotapes and perform competency checks, ratings-based adherence checks, and address any issues with instructors. Their feedback will be implemented in later sessions. Instructors will be required to complete a fidelity checklist for every class session they conduct.

Statistical Power

Power analysis. A target course section N of 36 (N=18 BA and N=18 SO), with N=432 participants total, will be required to detect medium effect sizes ($d=.43$) for main outcomes. Each class is expected to contain 18-20 students and power analyses were conducted assuming an 85% consent rate and a 20% attrition at follow up. An 85% consent rate will yield 15 participants per class, or N=540 total. With a 20% attrition rate, we will achieve the N=432 participants (12 per course section cluster) necessary to detect our outcomes of interest. For mediation analyses, will have sufficient power to detect a correlation between a drinking outcome and BA at a given time point $>.20$.

Data Analysis Plan

We will use SAS PROC Mixed with full information Maximum Likelihood estimation to evaluate outcomes using general linear mixed models for continuous outcomes and SAS PROC GLIMMIX for binary outcomes. Assignment to treatment condition will occur at the class section level (level 3). Student observations (level 1), will be nested in students (level 2), which will be nested within class sections. Fixed effects for intervention condition (BA or SO), instructor, and

cohort will be included at the class section level. Sex will also be added as a fixed effect at level 2. This approach will result in models with appropriate standard errors for the clustered sample.

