For aim 1 we will compare differences between BA vs control in likelihood of exceeding the clinical cut-off for risky drinking as a binary outcome, and alcohol consumption (AUDIT consumption questions) and alcohol-related problems (AUDIT problem questions) as continuous outcomes. In addition, we will test differences across conditions in high-intensity drinking. Separate models will be developed for each outcome. Of primary interest are the main effects of treatment condition on both the intercepts and slopes for each of the outcomes. For aim 3 exploratory analyses on stress, depression, and binge eating, outcomes will be modeled separately for each outcome using general linear mixed models.

Analyses will be conducted to determine whether changes in environmental reinforcement and delay discounting mediate the association between intervention condition and alcohol outcomes. Moderation analyses will be conducted to determine whether intervention efficacy depends on coping-motivated drinking at baseline, sex, or race/ethnicity.

References

1. Brown, S. A. *et al.* A Developmental Perspective on Alcohol and Youths 16 to 20 Years of Age. *Pediatrics* **121**, S290–S310 (2008).
2. Gruenewald, P. J. Regulating Availability: How Access to Alcohol Affects Drinking and Problems in Youth and Adults. *Alcohol Res. Health* **34**, 248–256 (2011).
3. Johnston, L. D. *et al.* *Demographic Subgroup Trends among Young Adults in the Use of Various Licit and Illicit Drugs, 1988-2016. Monitoring the Future Occasional Paper Series. Paper 89.* (Institute for Social Research, 2017).
4. Schulenberg, J. *et al.* *Monitoring the Future national survey results on drug use, 1975–2016: Volume II, College students and adults ages 19–55.* <http://monitoringthefuture.org/pubs.html#monographs> (2017).
5. Patrick, M. E. & Terry-McElrath, Y. M. High-Intensity Drinking by Underage Young Adults in the United States. *Addict. Abingdon Engl.* **112**, 82–93 (2017).
6. Patrick, M. E., Terry-McElrath, Y. M., Kloska, D. D. & Schulenberg, J. E. High-Intensity Drinking Among Young Adults in the United States: Prevalence, Frequency, and Developmental Change. *Alcohol. Clin. Exp. Res.* **40**, 1905–1912 (2016).
7. Nelson, T. F., Toomey, T. L., Lenk, K. M., Erickson, D. J. & Winters, K. C. Implementation of NIAAA College Drinking Task Force Recommendations: How Are Colleges Doing 6 Years Later? *Alcohol. Clin. Exp. Res.* **34**, 1687–1693 (2010).

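### Arm differences in intercepts are of primary interest but time zero is never defined; under the usual week-1 coding, four of the eight aim-1 contrasts say nothing about efficacy

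*Combined protocol and SAP*

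**What the plan says.** The Data Analysis Plan names four aim-1 outcomes. Three come from the AUDIT: "likelihood of exceeding the clinical cut-off for risky drinking as a binary outcome, and alcohol consumption (AUDIT consumption questions) and alcohol-related problems". The fourth is added next: "In addition, we will test differences across conditions in high-intensity drinking". On modelling it says "Separate models will be developed for each outcome", and then "Of primary interest are the main effects of treatment condition on both the intercepts and slopes for each of the outcomes".

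The data structure is a three-level repeated-measures model: "Student observations (level 1), will be nested in students (level 2), which will be nested within class sections". The covariates are listed as "Fixed effects for intervention condition (BA or SO), instructor, and" cohort at section level, and "Sex will also be added as a fixed effect at level 2". The plan names no time origin, time scale or shape of the time trend. It names neither a baseline-outcome covariate nor an equal-baseline constraint. Nothing removes week 1 from the response. In the analysis text, baseline is mentioned only for coping-motivated drinking as a moderator.

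The Assessment Schedule says "Participants will be assessed at three times during treatment (weeks 1, 7, and 15", followed by a 5-month follow-up for all participants. Under Alcohol Use and Problems, both instruments refer to the past month. Under Participant Recruitment and Enrollment, students are asked for consent in the first week of class, when their section already has its condition.

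**The concern.** In a growth model with time counted from the first assessment, the effect of condition on the intercept is the arm difference at that assessment. Here that is week 1. The BA content that week (Table 1) is the rationale and an introduction to daily monitoring, and a past-month report made then covers mostly time before the course. A difference at that point is chance, or it reflects who consented in each arm. It does not show that BA worked.

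The plan nevertheless gives it the same standing as the slope. A trial with a low week-1 mean in the BA arm and parallel trends afterwards could be reported as showing an effect of primary interest. Because time zero is not fixed, the meaning of four of the eight contrasts could also be settled after the data are seen. A lesser point is that the models do not use the week-1 outcome to sharpen the arm comparison.

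**Working it through.** **The plan's own figures.** 36 sections × 15 = 540 enrolled, and 540 × 0.80 = 432 analysed; both reproduce. The claim that 432 suffices for d = .43 cannot be checked, because alpha, power and ICC are not given. This point does not challenge the sample size.

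**Number of contrasts.** 4 outcomes × 2 parameters = 8, of which 4 are on intercepts.

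**Chance difference at week 1.** Inputs: 18 × 15 = 270 per arm and 15 per section (Statistical Power). The ICC is assumed.
- SE in SD units = √[2(1 + 14·ICC)/270].
- ICC 0: √(2/270) = 0.086; 95% range ±0.17.
- ICC .05: √(3.4/270) = 0.112; 95% range ±0.22.
- ICC .10: √(4.8/270) = 0.133; 95% range ±0.26.
- Relative to d = .43: 0.22/0.43 = 51% and 0.26/0.43 = 61%.

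Differential consent would come on top of these ranges.

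**Behaviour of the tests with no treatment effect.** 4,000 simulated trials per time origin, one outcome, assumed ICC .05 and within-student correlation .6:

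| Time origin | Intercept rejects | Slope rejects | Either rejects | Correlation of the two estimates |
|---|---|---|---|---|
| Week 1 | 4.7% | 4.4% | 8.7% | −0.26 |
| Week 15 | 4.6% | 4.8% | 9.2% | 0.01 |
| Follow-up | 4.8% | 5.3% | 9.5% | 0.41 |

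Each test holds its level, and having two per outcome roughly doubles the chance of a false positive. With week-1 coding, a chance imbalance in the intercept also carries over, with opposite sign, into the slope estimate.

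**Precision of the slope.** Assumptions: continuous outcome, compound symmetry with correlation ρ, linear time, and four visits at t = 0, 6, 14 and 34 weeks from week 1 (follow-up taken as about 20 weeks after week 15). The 17-month visit is left out, since only a random 20% of Years 2–4 attend it.
- Σt = 54, so (Σt)² = 2916. Σt² = 36 + 196 + 1156 = 1388. Σ(t − 13.5)² = 1388 − 2916/4 = 659.
- Separate week-1 means in each arm: slope variance ∝ (1 − ρ)/659.
- Common week-1 mean: slope variance ∝ (1 − ρ)/[1388 − 2916·ρ/(1 + 3ρ)].
- The ratio of the first to the second is [1388 − 2916·ρ/(1 + 3ρ)]/659.
- ρ = .5: (1388 − 583.2)/659 = 1.22, a reduction of 18% if avoided.
- ρ = .6: (1388 − 624.9)/659 = 1.16, a reduction of 14%.
- ρ = .7: (1388 − 658.5)/659 = 1.11, a reduction of 10%.
- The wider range is 1.41 at ρ = .3 to 1.07 at ρ = .8.

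**The case against.** The strongest reply is that the plan never says the intercept is week 1. A reader might infer it from the week-1 assessment, and it is the common default, but it remains an inference. With time centred at week 15 or at follow-up, the intercept is a post-treatment contrast and a legitimate efficacy question. This stands, and it makes the point conditional. It does not remove the point, because the plan does not adopt a later origin.

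A second reply is that baseline is not ignored. Week 1 appears to be one of the repeated observations, so the slope contrast already measures change from week 1. That stands too. The slope tests answer aim 1, and their only cost is a modest loss of precision. Nor is error inflated within any single test.

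A reader might also be tempted by two larger figures.
- With eight independent tests at 5% the chance of at least one false positive is 1 − 0.95^8 = 33.7%. The four slope tests alone still give 1 − 0.95^4 = 18.5%, so much of this concerns the missing multiplicity rule and not the intercept. Independence also overstates it, because three of the four outcomes come from one 10-item questionnaire.
- The two-time-point formula, (1 − ρ²)/[2(1 − ρ)], gives variance savings of 25% to 15% at ρ = .5 to .7. It compares baseline adjustment with a single change score, not with a four-visit slope, for which the saving is 18% to 10%.

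**Conclusion.** The point holds in conditional form. The plan gives intercept differences primary interest for four outcomes without defining the intercept. Under the usual coding from week 1, those four contrasts carry no evidence of efficacy, and a chance difference of up to about 0.22 SD (ICC .05) or 0.26 SD (ICC .10) could be presented as such. The harm is misinterpretation and four additional tests, not a faulty significance level.

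It would go too far to say that the plan tests baseline differences as efficacy, since the documents do not fix time zero. Nor do they use the term co-primary.

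The absence of the week-1 outcome as a covariate is certain from the listed fixed effects. Its cost is an efficiency matter: slope variance higher by about 22%, 16% or 11% at correlations of .5, .6 or .7. The ICC, these correlations, compound symmetry and the follow-up spacing are all assumptions, and the variance figures apply to continuous outcomes.

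**What to change.** Change the Data Analysis Plan as follows:
- State the time origin, scale and form of the time effect.
- State that an arm difference at week 1 is descriptive and is not an efficacy test.
- For each aim-1 outcome, take weeks 7, 15 and the 5-month follow-up as the response and specify one arm contrast in advance (for example the average over these visits, or a named visit). Adjust it for the student's week-1 value of that outcome and for the section mean of that value.

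This adjustment is preferable to constraining the arms to a common week-1 mean. Consent is sought after sections are assigned, so equal week-1 means among consenters cannot be taken for granted. The precision figures above were computed for that constraint, so they indicate the order of gain and not its exact size under covariate adjustment.

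The cost is SAP wording only, since the assessments are already scheduled. The section mean uses one section-level degree of freedom, and the text needs a rule for a missing week-1 value. Slopes can still be reported descriptively. Naming a single primary outcome and a multiplicity rule is a separate decision and is not needed for this change.

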The *Alcohol Use Disorder Identification Test (AUDIT)*¹⁶ is a 10-item questionnaire designed to assess hazardous drinking and related problems. The AUDIT provides a total score, with 8+ indicating hazardous use^{17,18}. The AUDIT has also been examined as two subscales: alcohol consumption (items 1-3 focused on frequency and quantity) and alcohol problems (items 4-10 that assess consequences)¹⁹⁻²¹. The percent of participants above the clinical cutoff for the total score will be used in analyses, as well as both subscale scores. While the AUDIT was originally designed to assess a time interval of the past 12 months, researchers have assessed change in alcohol use and related problems in shorter time intervals of 1, 3, and 6 months^{14,22}. The present study will use the past month as the reference point for the AUDIT.

The *computerized Time Line Follow Back (TLFB-C)* will be used to assess daily alcohol use in standard drinks during the past month²³⁻²⁵. The TLFB-C has good test-retest reliability and evidence of convergent validity with the TLFB administered in-person among college

student samples^{26,27}. Heavy drinking occasions will be defined as 4+ drinks for females, or 5+ for males in one episode, in excess of the low risk drinking guidelines from the National Institute on Alcohol Use and Alcoholism²⁸. High-intensity drinking occasions will be defined as double the heavy drinking occasion criteria, or 8+ for females and 10+ for males.

Reinforcement Processes

Environmental reinforcement. The Adolescent Reinforcement Survey Schedule - Alcohol Use Version (ARSS-AUV) assesses the frequency of past-month engagement in and enjoyment derived from 45 activities²⁹. Each question is posed twice - once to assess the frequency and enjoyment of the activity while using alcohol and the once to assess the frequency and enjoyment of the activity while not using alcohol. Frequency and enjoyment items are summed to form respective scores and then multiplied to form subscales for alcohol-related reinforcement and alcohol-free reinforcement. The two subscales are used to calculate the outcome, the total reinforcement ratio (TRR) between alcohol-related and alcohol-free reinforcement.

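### Aim 1 makes treatment effects on four overlapping alcohol outcomes of primary interest, with no primary outcome, primary contrast, alpha, multiplicity control or success rule

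*Combined protocol and SAP*

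**What the plan says.** The aim 1 paragraph of the Data Analysis Plan compares BA with SO on "likelihood of exceeding the clinical cut-off for risky drinking as a binary outcome", and on "alcohol consumption (AUDIT consumption questions) and alcohol-related problems (AUDIT problem questions) as continuous outcomes". It continues: "In addition, we will test differences across conditions in high-intensity drinking". Then: "Separate models will be developed for each outcome". The next sentence is "Of primary interest are the main effects of treatment condition on both the intercepts and slopes for each of the outcomes".

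The Measures section (Alcohol Use and Problems) shows how the first three outcomes are related. The AUDIT has 10 items, split into "alcohol consumption (items 1-3 focused on frequency and quantity) and alcohol problems (items 4-10 that assess consequences", and a total of 8 or more marks hazardous use. All three versions are analysed: "The percent of participants above the clinical cutoff for the total score will be used in analyses, as well as both subscale scores".

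The Statistical Power section gives one effect size, d=.43, "for main outcomes". Those outcomes are not named, and no alpha, power level, ICC or allowance for several tests is stated. In the Data Analysis Plan, aim 3 (stress, depression, binge eating) is labelled exploratory; aim 1 is not.

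**The concern.** Aim 1 carries the trial's efficacy question on alcohol. As written, a reader cannot tell which of up to eight test results answers it. With no designated outcome or contrast and no error control, the chance that at least one comes out significant when BA does nothing exceeds the nominal level for a single test.

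The overlap also affects interpretation. Consumption and problems together use all 10 AUDIT items, and the binary outcome is a cut on the total of the same items. Agreement among two or three AUDIT results is therefore not independent confirmation. Finally, an effect size quoted without allowance for several tests is too favourable for a claim that must survive correction.

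**Working it through.** **1. The plan's own figures.** From Statistical Power: 18 × .85 = 15.3, taken as 15 per class; 36 × 15 = 540; 540 × (1 − .20) = 432 = 36 × 12. These reproduce. The step from N=432 to d=.43 cannot be reproduced, because alpha, power and ICC are not given.

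**2. Number of tests.** Four outcomes with one contrast each give 4 tests. With intercept and slope for each, there are 8.

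**3. Independent tests.** Assume two-sided .05 per test and no true effect.
- Either direction: 1 − .95⁴ = 18.5%; 1 − .95⁸ = 33.7%.
- In BA's favour only (2.5% per test): 1 − .975⁴ = 9.6%; 1 − .975⁸ = 18.3%.

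**4. Correlated outcomes.** The document gives no correlation, so it is varied. For four equicorrelated normal test statistics with correlation ρ, the chance of at least one result in BA's favour is 1 − ∫ φ(u) [Φ((1.96 − √ρ·u)/√(1 − ρ))]⁴ du. The either-direction version uses both tails. With intercept and slope uncorrelated, P₈ = 1 − (1 − P₄)²; for example, at ρ = .5, 1 − (1 − .078)² = 15.0%.

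| ρ | BA's favour, 4 tests | BA's favour, 8 tests | Either direction, 4 tests | Either direction, 8 tests |
|---|---|---|---|---|
| 0 | 9.6% | 18.3% | 18.5% | 33.7% |
| .3 | 8.7% | 16.7% | 17.4% | 31.8% |
| .5 | 7.8% | 15.0% | 15.6% | 28.7% |
| .7 | 6.5% | 12.6% | 13.0% | 24.4% |
| .9 | 4.7% | 9.1% | 9.4% | 17.8% |

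Simulation with 2 million draws agrees within 0.1 percentage point. At ρ = .5, an intercept–slope correlation of −.5 changes the eight-test figures to 26.8% (either direction) and 15.5% (BA's favour).

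**5. Effect on d=.43 (illustration only).** Assumptions: 216 per arm, 12 per section, a t-test on 36 − 2 = 34 df that ignores the instructor, cohort and sex terms, SE(d) = √(2·DEFF/216) and DEFF = 1 + 11·ICC. The first Holm step across four is .05/4 = .0125.
- If d=.43 was set at 80% power: the required noncentrality is 2.884, so SE = .43/2.884 = .149, DEFF = 2.40 and ICC = 1.40/11 = .127. At .0125 the required noncentrality is 3.501, so d = 3.501 × .149 = .52. Power for d=.43 is 60%.
- If it was set at 90% power: noncentrality 3.337, SE = .129, DEFF = 1.79, ICC = .072. At .0125, noncentrality 3.964 gives d = .51 for 90% power. Power for d=.43 is 75%, and d for 80% power is .45.

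The 60% and 75% are worst cases, for an effect on one outcome alone. If other outcomes also respond, later Holm steps are less strict.

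**The case against.** A reader might infer that BA has a 15% to 29% chance of being declared effective when it does nothing. The documents do not support that. Those figures count significant results in either direction, and a result showing BA worse than SO would not declare it effective. They also depend on an assumed alpha and an assumed correlation near .5. Shared AUDIT items argue for a higher correlation, which lowers the figures: at .7, the BA-favouring rates are 6.5% and 12.6%.

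The count of eight is also open to challenge. Time coding is not stated. If time is zero at week 1, the intercept contrast is a baseline difference and four slope tests remain.

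Nor does the plan say that one significant outcome suffices. Each model could be reported as its own conclusion, and the any-one-wins rule is inferred from silence. High-intensity drinking is introduced as an addition, and the sentence about primary interest describes effects rather than formally labelling endpoints.

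These objections limit the size but do not remove the gap. The sentence on primary interest follows the mention of high-intensity drinking and excepts no outcome. Dropping that outcome still leaves three uncorrected AUDIT tests, with 12.5% in either direction at correlation .5. No other section supplies a primary outcome, correction or success rule.

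It is likewise tempting to say that the trial's true detectable effect is d=.52. That figure needs 80% power and a back-solved ICC, neither of which is in the plan.

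**Conclusion.** The point stands as a missing decision rule for aim 1, with moderate inflation whose exact size the documents do not determine. With two-sided .05 per test, no true effect and intercept and slope uncorrelated, the chance of at least one result in BA's favour over correlations 0 to .9 is about 5–10% for four tests and 9–18% for eight, against 2.5% for one test. At correlation .5 it is about 8% and 15%, or about three to six times the single-test rate. The either-direction figures at that correlation are about 16% and 29%. The eight-test figures hold only if the intercept contrast is read as a treatment effect. Inflation appears at every correlation tried. The loss of detectable effect under correction is conditional on the power level behind d=.43, which the sponsor must supply.

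**What to change.** Before outcomes are seen, amend the aim 1 paragraph of the Data Analysis Plan as follows.
- State the time coding and define one condition contrast per outcome. Examples are condition-by-time over the scheduled assessments, or the condition difference at one named post-baseline assessment.
- Choose one error-control scheme. Either apply Holm across the four outcomes at two-sided .05, or name one primary outcome, of the sponsor's choice, at .05 and make the other three secondary under Holm.
- Claim an effect only where the chosen scheme supports it. Report all other aim 1 contrasts with confidence intervals as descriptive.

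In Statistical Power, state the alpha, power and ICC behind d=.43, and name the outcomes it covers. If Holm across four is chosen, restate the detectable effect at the first step (.0125) from those inputs; the .51 and .52 shown above are conditional illustrations, not figures to copy in.

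The cost is wording only, with no new data or participants. Holm across four gives a less favourable detectable effect. A single named primary leaves d=.43 unchanged for the primary test. Other schemes, such as a fixed testing order or a joint test, would also close the gap if fully specified.
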